Neuroimaging predictors of relapse during treatment for Opiate dependence

NCT: 02696096

June 22, 2017

C1. Brief Description of Subjects

The study sample will consist of 72 opiate dependent persons, 21-50 years old, who want to initiate buprenorphine treatment.

C2. Study Design

Participation for all individuals will last 4 months. Assessments will occur at baseline, and weeks 1, 4, 8, and 12. FMRI scans will occur on the initial study day (consent and BL assessment are also completed on this day) or within a week of the initial study day, and approximately 2-3 days later. Buprenorphine induction will begin at the completion of the second scan; follow-up medical visits will align with study assessments on weeks 1, 4, 8 and 12. All participants will receive 16 weeks of buprenorphine (the final 4 of these 16 weeks will include a taper).

C3. Specific Procedures or Treatments

Assessments: Participants will meet with the Research Assistant (RA) at the baseline visit, during the scanning sessions, and prior to the medical visit at weeks 1, 4, 8, and 12 after beginning buprenorphine. The goal of the follow-up contacts will be to assess drug and buprenorphine use using the TLFB, dispense buprenorphine, and biochemically confirm acute abstinence with urine toxicological analysis.

During the baseline (first study visit) day, participants will be cabbed to Butler Hospital to complete informed consent, meet with the study physician to confirm study eligibility, and complete the baseline assessment. If their FMRI is the same day, they will then be cabbed to the FMRI facility, where they will meet with a second research staff member and complete the FMRI session. At the conclusion of this first day, they will be cabbed home. If their FMRI is on a separate day from the BL appointment, they will be cabbed home from the BL appointment, then cabbed back and forth to the FMRI facility for the first FMRI. For all participants, for the second FMRI day, they will be cabbed directly to and from the FMRI facility. For the study visits during weeks 1-12, which all take place only at Butler Hospital, they will be asked to provide their own transportation.

Assessments will include the following measures: general demographic information, social support (Duke Social Support Index⁷⁸), self-efficacy (Thoughts About Abstinence Scale⁷⁹), other drug use (Addiction Severity Index section on drug use⁸⁰, self-report by TLFB, and urine toxicology), alcohol use, craving⁸¹ (Brief Substance Craving Scale⁸²), withdrawal symptoms (Clinical Opiate Withdrawal Scale⁸³), delayed discounting (paper version), and service utilization (The Treatment Services Review which quantifies types of treatment services received by participants⁸⁴ during treatment, including the number of 12-step groups attended).

This study will use Care New England's instance of REDCap for the collection and storage of data. The study will not collect or store any actual data within REDCap until the project has been moved into REDCap's production environment.

REDCap is a secure, web-based application developed by Vanderbilt University for building and managing surveys and databases. It is primarily designed to support online or offline data capture for research studies, quality improvement, and operations. REDCap provides easy data manipulation (with audit trails for reporting, monitoring and querying patient records), real-time data entry validation, and an automated export mechanism to common statistical packages.

Care New England's instance of REDCap is hosted within the Care New England data center in Warwick, RI. This REDCap instance is role-based and is fully integrated with CNE's Active Directory structure. It enjoys 24/7/365 enterprise-level support and security inherent to CNE's HIPAA-compliant data center. Network transmissions (data entry, survey submission, and web browsing) to and from REDCap are protected via TLS 1.2 encryption. REDCap's data is stored on encrypted servers within CNE's data center.

The REDCap Consortium is composed of thousands of active institutional partners in over one hundred countries who utilize and support REDCap. REDCap was developed specifically around HIPAA-Security guidelines, and more information about the consortium and system security can be found at <http://www.projectredcap.org/>.

Buprenorphine: The participant will meet with the study physician ([name]) at the first study visit at Butler Hospital, prior to buprenorphine induction. During this visit, he will take a medical history, confirm the participant's eligibility for buprenorphine and explain how to use the buprenorphine medication. Participants will be told at this first visit that they need to be in mild to moderate opiate withdrawal when they complete the second FMRI scan at the upcoming study visit (2-3 days later) in order to be eligible to receive their initial buprenorphine dose. At the conclusion of this second scan, research staff at the FMRI facility will complete the COWS to confirm withdrawal symptoms, remind the participant how to self-dose the buprenorphine, and provide the participant with enough buprenorphine to last until the next study visit in about a week.

As their initial buprenorphine dose, the participant will receive four milligrams of buprenorphine (with 1 mg of naloxone) sublingually¹⁴. Following this protocol, which [name] has used in multiple prior studies^{14,15}, additional buprenorphine will be taken home for use later in the day, with the usual first day dose of 16 milligrams (with 4mg naloxone), and 16 mg administered daily throughout the 12 weeks of maintenance for standardization. Participants will be seen and dosed by [name] thereafter with only enough buprenorphine provided at each study visit to reach the next scheduled medical visit. Buprenorphine dosing will be done with the understanding that a total of 16 weeks of treatment will be offered. Thus, at the week 12 visit, a buprenorphine taper will begin, with a reduction of half the week 12 dose during week 12-14, and the remaining taper during weeks 14-16. Upon request, participants will be provided with a complete list of buprenorphine providers in the area to continue buprenorphine assisted therapy (maintenance) if participants wish to continue treatment beyond the study period. For those participants continuing buprenorphine assisted therapy with a buprenorphine provider arranged post-study, a stable dose of buprenorphine will be provided during weeks 12-16 in lieu of taper. If the participant's appointment with this outside buprenorphine provider is after, but within approximately 10 days of, the 4-month study date, when the study medication is completed, the participant can be eligible to receive a "bridge prescription" to maintain continuity of medication between the end of the study and the start of outside care. Urine toxicology will be performed at each medical visit. No participant will be discharged for use of illicit opiates. Thus, the incentive to misrepresent opiate use behavior at follow-up assessments is relatively low since use does not result in discontinuation of buprenorphine or from the study, or loss of monetary compensation for assessment.

FMRI: For FMRI session 1, research staff will be certain that participants are not in opiate withdrawal (scoring <7 on the Clinical Opiate Withdrawal Scale⁸³). For FMRI session 2,

participants will be instructed to stop using opiates 12-24 hours prior to the session so they arrive at the Brown University FMRI facility at the time of their scan in a state of mild opiate withdrawal, scoring 7-12 on the Clinical Opiate Withdrawal Scale (COWS)⁸³. This COWS score range will allow standardization of withdrawal symptoms across opiate types (e.g., heroin, oxycodone). If they appear at the FMRI appointment and are not in withdrawal, participants will need to reschedule their scan. Participants will remain in withdrawal throughout the FMRI session 2 procedures, and after this FMRI will receive their first dose of buprenorphine. This plan is in keeping with the fact that withdrawal symptoms are essential for buprenorphine to be initiated.

After administration of pre-scan measures, participants will be “trained” to perform each of the three FMRI tasks, that is, made aware of what they will see and be asked to do when in the FMRI scanner. This training takes 15 minutes. Despite training, performance below chance level on the WM task and invalid responses on the DD task are expected in a small minority of participants, making the data from these individuals unusable. Resting state scans are not based on performance levels or subjective responses and therefore (unless data are lost to movement) always analytically adequate. Based on our experience administering these paradigms and the careful participant screening procedures that we have developed, we expect that analytic exclusions based on head movement and the inability of the participants to complete any particular FMRI portion of the study will be approximately 20%.

Participants will then apply earplugs and FMRI-compatible vision correction, if needed, and lie on the MR scanner table. Stimuli will be back-projected with a LCD projector onto a screen that the participant will view through mirrors fixed to the scanner. High-resolution T1 scans will be acquired before FMRI. During FMRI, participants will respond using a response box. The FMRI scan process will last approximately 60 minutes.

During both FMRI sessions, we will administer three FMRI behavioral challenges and a resting scan during the 60-minute protocol (see Table 1). Research staff will be overseen by co-Investigator [name], who will be responsible for administering the paradigms during FMRI data acquisition.

Table 1. FMRI Paradigms and domains challenged

Paradigm	Relapse Risk Domain(s)	Time	Bilateral ROIs
Delay Discounting (DD)	Reward, Impulsivity, Restraint	16 min	MFG, anterior insula, ACC, PCC, MedFG
Working Memory (WM)	WM, WM Cognitive Persistence	8 min	MFG, IPL, SMA
Inhibitory Control (IC)	Inhibitory Control	12 min	
Rest	Default Network	6 min	PCC, MedFG

Abbreviations: Middle frontal gyrus (MFG), anterior insula (AI), anterior cingulate (ACC), posterior cingulate (PCC), medial frontal gyrus (MedFG), inferior parietal lobule (IPL), supplementary motor area (SMA), ventral striatum (VS).

Delay Discounting Paradigm. This paradigm will be presented to examine decision-making for smaller immediate rewards versus larger delayed rewards. Thus, this task will assay impulsive choice preferences and the relative activity of both motivational drive and inhibitory control prior to entering buprenorphine treatment. Using an event-related design, participants make choices between smaller immediate rewards or larger delayed rewards over 72 trials (e.g., “Would you rather have \$25 today or \$35 in 29 days”). Each item has a temporal discounting function and the overall array of responses permits calculation of an individuals’ discounting level.

Working Memory Paradigm. The 2-Back version of the n-Back has been widely used in fMRI experiments as a WM challenge (i.e., a construct that refers to the process of short-term storage and management of information). This task challenges persistence during a sustained cognitive set since information is constantly maintained and updated over six 45s blocks of time. During the 2-Back WM challenge a series of 15 consonants are presented visually, one every 3000 ms. Participants make a yes/no response following each consonant - whether it is the same as, or different from, the consonant presented two earlier. Each consonant block contains 33% stimulus-target consonants pairs, which randomly overlap (e.g., F, N, B, **N**, **B**, K, **B**, **K**, N...). The *0-Back task* (a control task for the 2-Back) will include nine consonants presented at the standard 3000 ms rate. Subjects respond "yes" when a predetermined target consonant appears and "no" for other consonants. In total, there will be two runs of six 2-Back blocks each, requiring 4.8 minutes to complete (including control blocks). Three blocks of the 0-Back and three blocks of the rest will be included in each run. Accuracy and reaction time will be used as dependent measures of cognitive performance.

Go/No-Go: The Go/No-Go is an inhibitory control task. The version used in this study is similar to the version used previously by Kiehl and colleagues (2000), except that the Go stimuli are randomly selected letters other than "X". Specifically, letters will be presented for 100 ms each, with an interstimulus interval of 900 ms. A total of 240 letters will be presented consisting of 80% "Go" stimuli (all letters other than "X") and 20% "no-go" stimuli ("X"). Participants will be instructed to press a button for each "Go" stimulus in order to establish a pre-potent response, and inhibit their response when an "X" appears on the screen. Total percentage correct, percentage of false alarms (commission errors), and reaction times for correct go stimuli will be used as behavioral measures of performance.

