Aim 1. 1) Altered response to targeted challenges. These hypotheses will be tested using independent samples t-tests using mean task-associated activity in each ROI (listed in Table 1) as the dependent measure. For contrasts of cognitive persistence during the WM challenge, a linear mixed effects model for repeated measures will be conducted that allows estimates of contrasts of group over time and interactions. Parallel contrasts of behavioral measures will also be conducted for each task. 2) Disorganization of neural networks. Functional connectivity analyses will be conducted to determine the strength of relationships between the nodes of each network listed in Table 1. These will be converted to z-scores using Fisher's transformation and contrasted across groups using independent samples t-tests. 3) Compensatory mechanisms. Compensatory overactivation will be assessed using voxel-wise independent samples t-tests. Voxel threshold will be $<.05$ corrected for multiple comparisons. We expect more recruitment of regions outside of the *a priori* ROIs among the lapsers during all fMRI paradigms. Although assessed qualitatively due to a lack of *a priori* spatial extent, we will count both clusters of significant activity and total volume of significant activity outside of *a priori* ROIs in order to perform exploratory group contrasts. Compensatory underactivation will be assessed using independent samples t-tests of mean task-related responses (i.e., DD, WM, WMCP, IC) in regions identified as the DN in the independent functional connectivity analyses of the resting state imaging run. We expect that while fMRI predictors for lapse and relapse will be related, they will not be identical. We plan primary analyses to separately examine both lapse and relapse. Although they are strongly associated, this permits identification of differential relationships between each and fMRI challenges, if present. Prediction and prevention of relapse is the most important goal of this line of research; however, we still include lapse, since it has been used as the outcome measure in most relevant studies.

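### The Aim 1 connectivity t-tests make no allowance for residual head motion or, at rest, for wakefulness, so a group difference in either could be read as network disorganisation

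*Protocol*

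**What the plan says.** Protocol C3 (FMRI) explains that task data can become unusable through below-chance working-memory performance or invalid delay-discounting responses. It then says of the rest run: "Resting state scans are not based on performance levels or subjective responses and therefore (unless data are lost to movement) always analytically adequate". The next sentence gives the forecast loss: "analytic exclusions based on head movement and the inability of the participants to complete any particular FMRI portion of the study will be approximately 20" per cent. No movement threshold is given. Protocol Table 1 lists the rest run as 6 minutes, domain "Default Network", with posterior cingulate and medial frontal gyrus as regions.

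SAP C4, Aim 1 part 2, states: "Functional connectivity analyses will be conducted to determine the strength of relationships between the nodes of each network listed in Table 1". The test follows: "These will be converted to z-scores using Fisher's transformation and contrasted across groups using independent samples t-tests". The groups are defined by lapse within one week, or by a median split of time to lapse if group sizes are too unequal, and then by relapse. The markers are evaluated both in stable use and in withdrawal.

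Aim 1 part 3 tests task responses within "regions identified as the DN in the independent functional connectivity analyses of the resting state imaging run".

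The Aim 2 covariates are gender, age, social support, self-efficacy, comorbid alcohol and drug use, and mood. Neither motion nor wakefulness is named.

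**The concern.** The protocol's reason for counting rest runs as usable is that they have no performance component. For the same reason, the rest run has no behavioural sign that the participant stayed awake. The only stated safeguard is loss of the run to movement, and that does nothing about motion in the runs that are kept. Such motion can alter the correlation between regions, which is the quantity being tested.

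Lapsers and nonlapsers are not randomised groups. Any difference between them in residual motion or drowsiness goes straight into an unadjusted t-test. The first session requires a low withdrawal score, which does not establish alertness. In the second session participants stay in withdrawal throughout, and severity can vary within the permitted range. A difference is therefore conceivable in either session, and the plan reports nothing that would reveal one.

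At stake is one of the three Aim 1 markers: a positive connectivity result could not be separated from an artefact.

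**Working it through.** The documents give no power, effect size, SD or alpha for these tests, so there is no planned figure to reproduce. The check asks how far a plain t-test departs from its nominal level if the groups differ in motion but not in true connectivity.

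**Inputs from the documents**
- Sample size 72 (Protocol C1).
- About 20% imaging exclusions (Protocol C3): 72 x (1 - 0.20) = 57.6, taken as 57, or 29 v 28 if split evenly.

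**Assumed inputs**
- Two-sided alpha of 5%.
- d, the lapser-nonlapser difference in residual motion among retained scans: 0.3, 0.5 or 0.8 SD.
- r, the within-group correlation of residual motion with connectivity: 0.2, 0.3 or 0.4.
- True connectivity difference of zero.

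**Formulae**
- Spurious shift in connectivity, in within-group SDs: r x d.
- Noncentrality: r x d / sqrt(1/29 + 1/28) = r x d / 0.265.
- False-positive rate: probability that a noncentral t on 55 degrees of freedom falls outside the central 5% limits.

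For example, d = 0.5 and r = 0.3 give a shift of 0.15 SD, noncentrality 0.15 / 0.265 = 0.57, and a rate of 8.6%.

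**False-positive rate, 29 v 28**

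| d | r = 0.2 | r = 0.3 | r = 0.4 |
|---|---|---|---|
| 0.3 | 5.6% | 6.3% | 7.3% |
| 0.5 | 6.6% | 8.6% | 11.5% |
| 0.8 | 9.1% | 14.5% | 22.1% |

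If d = 0 the rate is 5% whatever r is.

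**Sensitivity to group size.** Over the same grid, an uneven 17 v 40 split gives 5.5% to 19.2%. If no one were excluded (36 v 36), the range would be 5.7% to 26.8%.

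**Scale.** At 29 v 28, the true difference detectable with 80% power is about 0.76 SD. The spurious shifts in the table run from 0.3 x 0.2 = 0.06 SD to 0.8 x 0.4 = 0.32 SD.

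**Effect of adjustment.** In 20,000 simulated null trials per setting (29 v 28), adding motion as a covariate gave:

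| d, r | Plain t-test | Motion-adjusted |
|---|---|---|
| 0.3, 0.3 | 6.6% | 5.0% |
| 0.5, 0.3 | 8.4% | 5.2% |
| 0.8, 0.4 | 21.9% | 5.0% |

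This assumes that motion is measured without error and acts linearly. Sleep was not modelled.

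**The case against.** **The adequacy sentence is mainly a forecast of data yield.** It sits between a remark on unusable task data and the exclusion estimate, and it excepts movement losses. A reader might infer a deliberate policy of leaving motion uncorrected. The documents do not support that: the supplied text has no image-processing section for any run, and motion correction may be described elsewhere. This stands. What remains is that the group test, as written, has no motion term.

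**Nothing shows that lapsers move or doze more.** This also stands. A reader might infer that such differences are likely in this population, but the documents hold no motion, sedation or sleep data by lapse status. The movement exclusion would also limit residual motion, to a degree that cannot be judged without a threshold.

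**The default-network regions.** A reader might infer that a contaminated rest run carries a false group difference into the underactivation tests. The text does not support this. Those tests use task responses, and the rest run only locates the regions. If the regions are common to both groups, poor location would mainly dilute or misplace the contrast. Nothing says that they are derived separately by group.

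**Sleep has limited reach.** Agreed: it bears mainly on one 6-minute run, because the tasks require button responses. Motion bears on every network.

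**Adjustment may remove real signal.** If restlessness partly expresses impulsivity or poor inhibitory control, which the study targets, a motion-adjusted contrast could over-correct. This is a sound reason to report both analyses rather than replace one with the other.

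**Conclusion.** The point holds as a conditional weakness. Connectivity is compared between outcome-defined groups with no allowance for residual motion in any network, or for wakefulness in the rest run. If the groups differ in either, the stated test cannot distinguish an artefact from network disorganisation. The size is unknown. On the assumed inputs the false-positive rate runs from about 5.6% to 22%, and there is no inflation if the groups do not differ in motion. These figures illustrate motion only; they do not estimate what will happen in this study, and the direction of any bias is not established. The change is worth making because it is cheap and the displacement table would show whether the problem exists.

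**What to change.** - **SAP, Aim 1 part 2:** beside each unadjusted t-test, report a group comparison of Fisher-z connectivity adjusted for each participant's mean frame-to-frame displacement in that run. Tabulate displacement by group and session.
- **Protocol C3:** qualify the adequacy statement, so that a rest run not lost to movement is described as unaffected by task performance and still subject to checks on residual motion and wakefulness.
- **Rest run:** where scanning is still under way, ask one question afterwards on whether the participant fell asleep, and repeat the resting contrasts without those who did.
- **SAP, Aim 1 part 3:** state that the default-network regions are defined from both groups pooled.

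Displacement comes from standard image realignment, so the motion part can also be applied to scans already acquired. The cost is SAP wording, one question per scan, one degree of freedom per adjusted contrast, and slightly fewer rest runs in the sensitivity analysis. The main downside is possible over-adjustment if motion partly expresses the trait under study, which is why both results should be shown.

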Neuroimaging predictors of relapse during treatment for Opiate dependence
NCT: 02696096
June 22, 2017

C4. Data Analysis

A priori ROI analyses will be our primary method for quantifying task-related effects for hypothesis testing, while analyses involving the functionally defined ROIs will serve to validate our *a priori* findings.

We will test hypotheses using lapse as the grouping variable and then with relapse. Three markers (altered response, disorganized response, and compensatory mechanisms; see Aim 1) will be evaluated in both the stable opiate use state and during opiate withdrawal.

We will compare lapsers and nonlapsers on pre-quit behavioral and fMRI measures hypothesized to predict lapse (Aim 1) followed by application of Cox regression models predicting time to relapse among the full sample to determine if neuroimaging measures provide additional utility in predicting lapse (Aim 2). Although Aim 1 hypotheses are designed to be tested as group contrasts based on lapse within 1 week of quitting, we will group by median split of time to lapse if this results in unacceptable differences in group size.

Aim 1. 1) Altered response to targeted challenges. These hypotheses will be tested using independent samples t-tests using mean task-associated activity in each ROI (listed in Table 1) as the dependent measure. For contrasts of cognitive persistence during the WM challenge, a linear mixed effects model for repeated measures will be conducted that allows estimates of contrasts of group over time and interactions. Parallel contrasts of behavioral measures will also be conducted for each task. 2) Disorganization of neural networks. Functional connectivity analyses will be conducted to determine the strength of relationships between the nodes of each network listed in Table 1. These will be converted to z-scores using Fisher's transformation and contrasted across groups using independent samples t-tests. 3) Compensatory mechanisms. Compensatory overactivation will be assessed using voxel-wise independent samples t-tests. Voxel threshold will be $<.05$ corrected for multiple comparisons. We expect more recruitment of regions outside of the *a priori* ROIs among the lapsers during all fMRI paradigms. Although assessed qualitatively due to a lack of *a priori* spatial extent, we will count both clusters of significant activity and total volume of significant activity outside of *a priori* ROIs in order to perform exploratory group contrasts. Compensatory underactivation will be assessed using independent samples t-tests of mean task-related responses (i.e., DD, WM, WMCP, IC) in regions identified as the DN in the independent functional connectivity analyses of the resting state imaging run. We expect that while fMRI predictors for lapse and relapse will be related, they will not be identical. We plan primary analyses to separately examine both lapse and relapse. Although they are strongly associated, this permits identification of differential relationships between each and fMRI challenges, if present. Prediction and prevention of relapse is the most important goal of this line of research; however, we still include lapse, since it has been used as the outcome measure in most relevant studies.

Aim 2. For each targeted relapse-risk domain, comparisons of behavioral and fMRI markers will be examined per ROI using logistic regression (lapse) and Cox proportional hazards survival models predicting time to relapse conditional on planned covariates including gender, age, social support, self-efficacy, *comorbid alcohol and drug use*, and mood. The unique explanatory contribution of fMRI responses will be evaluated by comparing a full model (including fMRI response, behavioral data acquired during the fMRI challenges, and covariates) to a reduced model, which includes only the behavioral data and covariates.

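### Aim 2 asks whether fMRI adds to prediction, but plans only a nested-model comparison in the fitting sample, which tests association and does not measure prediction

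*SAP*

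**What the plan says.** SAP section C4 (opening paragraphs) describes the "application of Cox regression models predicting time to relapse among the full sample" and gives the purpose as "to determine if neuroimaging measures provide additional utility in predicting lapse (Aim 2". The Aim 1 paragraph ranks predicting and preventing relapse as the main goal of this line of research, and the study title speaks of predictors.

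The Aim 2 paragraph gives the method. Markers are "examined per ROI using logistic regression (lapse) and Cox proportional hazards survival models predicting time to relapse". The adjustment set is described as "conditional on planned covariates including gender, age, social support, self-efficacy", with alcohol and drug comorbidity and mood also listed. "The unique explanatory contribution of fMRI responses will be evaluated by comparing a full model" (fMRI, task behaviour and covariates) "to a reduced model, which includes only the behavioral data and covariates".

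Neither document names a comparison statistic, a discrimination or calibration measure, a hold-out set, cross-validation, bootstrap correction or shrinkage. The only validation mentioned is a repeat analysis with functionally defined regions, for which no new participants are described. The only multiplicity control stated is for the voxel-wise test in Aim 1.

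**The concern.** The purpose and the method answer different questions. A nested comparison asks whether the fMRI term explains outcome variation beyond behaviour and covariates. Predictive utility asks whether a model that includes fMRI would rank new patients better than one without it. In a small sample with many terms, these can diverge.

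As written, a significant fMRI term could be reported as added predictive utility when no prediction has been measured. If an AUC or C-index were added at the reporting stage without correction, it would flatter both models. Aim 2 is also run separately for each region and in two opioid states, so some regions are likely to stand out by chance.

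**Working it through.** The plan gives no AUC, C-index, event rate, effect size or Aim 2 significance level, so there is no figure of its own to reproduce. The check counts the inputs and then simulates the planned comparison.

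**Inputs from the documents**
- Enrolled: 72 (Protocol C1: "The study sample will consist of 72 opiate dependent persons, 21-50 years old").
- Expected fMRI exclusions (Protocol C3, FMRI): "inability of the participants to complete any particular FMRI portion of the study will be approximately 20" per cent. Analysable: 72 × 0.8 = 57.6, about 58.
- Model terms: six listed covariates, or seven if alcohol and drugs are separate; the list is open-ended. With at least one behavioural term the reduced model has 7–8 terms, and with one fMRI term the full model has 8–9.
- Candidate markers: Protocol Table 1 shows 5 + 3 + 2 = 10 paradigm-by-region pairs, with the inhibitory-control cell blank. Two states give 10 × 2 = 20, before counting two outcomes.

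**Assumptions (not in the documents)**
- Set-up A: n = 58; lapse 25% or 50%; 8 reduced-model terms, two real (log-OR 0.4 per SD), plus one fMRI term. Cox version: 50% or 70% events, two real terms (log-HR 0.3).
- Set-up B: n = 57; 40% lapse; 9 reduced-model terms, three real (log-OR 0.35), plus one fMRI term.
- Set-up A uses independent predictors and a 1-df likelihood-ratio test at 0.05. Apparent figures come from the fitting sample and true figures from a large independent sample.

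**Events per term** (8 terms): 58 × 0.25 / 8 = 1.8 to 58 × 0.50 / 8 = 3.6.

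**Absolute discrimination, full model**

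| Scenario | Apparent | True |
|---|---|---|
| Logistic, set-up A, n = 58 | 0.77–0.81 | 0.58–0.62 |
| Logistic, set-up A, n = 72 (no exclusions) | 0.74–0.79 | 0.58–0.64 |
| Logistic, set-up B, null marker | 0.79 | 0.59 |
| Logistic, no real predictor at all | 0.73 | 0.50 |
| Cox C-index, n = 58 | 0.68–0.71 | 0.57–0.62 |

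**Gain from fMRI (full minus reduced), one prespecified marker**

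| Marker | Apparent | True |
|---|---|---|
| Null, logistic | +0.010 to +0.015 | −0.004 to 0.000 |
| Weak, log-OR 0.3 | +0.022 | +0.014 |
| Solid, log-OR 0.5 | +0.037 to +0.041 | +0.040 to +0.048 |
| Null, Cox | +0.007 to +0.008 | −0.005 to −0.003 |
| Log-HR 0.4, Cox | +0.034 | +0.040 to +0.046 |

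Set-up B agrees: null +0.010 against −0.005, weak +0.022 against +0.015, log-OR 0.5 +0.035 against +0.045.

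**Gain when only significant results are kept** (set-up A, 50% lapse): null +0.054 against −0.016; log-OR 0.3 +0.058 against +0.025; log-OR 0.5 +0.069 against +0.055.

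**Best of 20 null candidates:** apparent gain +0.053 to +0.059 against about −0.015. At least one was nominally significant in about 82% of simulated studies. With 20 independent tests at exact 5% size, the figure is 1 − 0.95^20 = 64%. The rest reflects the test's own size of about 7–8%: 1 − 0.92^20 = 81%.

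**Effect of bootstrap optimism correction**
- Set-up A, null marker: full-model AUC 0.761 becomes 0.623 (true 0.584); gain +0.013 becomes +0.003 (true −0.007).
- Set-up A, log-OR 0.5: full-model AUC 0.793 becomes 0.671 (true 0.617); gain +0.033 becomes +0.032 (true +0.040).
- Set-up B, null marker: full-model AUC 0.79 becomes 0.64 (true 0.59).
- Set-up B, only null markers that reached p < 0.05: bootstrap-corrected gain +0.055, cross-validated gain +0.063, true gain −0.019. Correcting a region after it has been selected does not remove the selection bias.

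**The case against.** The Aim 2 paragraph names its target as an explanatory contribution, and a nested comparison is a legitimate test of that. With a likelihood-ratio test, a single prespecified null marker was rejected in about 7–8% of logistic simulations, which is only mildly anti-conservative. The plan proposes no prediction rule and commits to no AUC, so the optimism concerns a number it does not yet produce. Predicting, in the opening paragraphs, may mean only that the measures precede the outcome. All this stands as a defence of the test. It does not supply evidence for the stated purpose, which is predictive utility.

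A reader might infer that the in-sample gain from fMRI is always overstated. Nothing supports that. The documents define no gain measure, and for a prespecified marker at log-OR 0.5 the apparent gain was on average no larger than the true one. At log-OR 0.7 in set-up B it was smaller (+0.047 against +0.073). A reader might also take the contrast of +0.054 with −0.016 as the size of the bias. It is conditional on a false positive, so it is mainly a multiplicity problem.

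The low true AUCs partly reflect the assumed weak covariates. In set-up B even the perfectly known model reaches only about 0.66. The levels are therefore illustrative, and optimism is smaller in the Cox analysis of relapse. The gap between apparent and true discrimination nevertheless appeared in every scenario, including n = 72.

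**Conclusion.** The mismatch is real: Aim 2 is framed as prediction, and the only planned method tests association in the fitting sample. At about 58 participants and 8–9 or more terms, uncorrected discrimination would be too high by about 0.2 AUC for lapse (0.79 − 0.59 = 0.20 in set-up B). For relapse the excess is about 0.1 in C-index (for example 0.712 − 0.601 = 0.11). The gain from fMRI is overstated for null or weak markers and for regions picked out by significance, but not on average for one prespecified marker with a solid effect.

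The direction for absolute discrimination is secure. The sizes rest on assumed lapse and relapse rates, effect sizes, independent predictors and one degree of freedom per term. The 82% figure would be lower if regions are positively correlated. The point should be settled before analysis, because it decides what Aim 2 may conclude; it does not invalidate the nested comparison.

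**What to change.** 1. Keep the full-versus-reduced comparison as the test of explanatory contribution, name the statistic, and control multiplicity across the per-region, two-state Aim 2 tests.
2. Report AUC (lapse) and C-index (relapse) for the full and reduced models, and their difference. Use bootstrap optimism correction or repeated cross-validation, repeating every modelling and region-selection step inside each resample, and give intervals.
3. Describe findings as association unless the corrected figures and their interval support a predictive statement. State that optimism correction alone does not remove the bias from reporting only significant regions.
4. Align the opening of section C4, which ties Cox models of relapse to a conclusion about lapse, with the Aim 2 paragraph, which uses logistic regression for lapse.

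The cost is SAP wording and analysis code, with no new participants or scans. Prediction figures will be less favourable. In set-up B the corrected change in AUC had an SD of about 0.05 around a true gain of about 0.045 at log-OR 0.5. A rough 95% range is 0.045 ± 1.96 × 0.05, or about −0.05 to +0.14, so a real marker may remain inconclusive for prediction. For that reason the corrected change should qualify the predictive claim and should not replace the association test.
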